## 6.2. Primary Efficacy Endpoint and Analysis

### 6.2.1. Definition

The primary efficacy endpoint is the mean change from baseline (baseline period) in the monthly average number of headache days of at least moderate severity during the 12-week period after the first dose of the IMP.

The primary efficacy endpoint for this study will be derived from PTH data (presence of headache [yes/no] and peak severity [mild/moderate/severe]) collected daily using an electronic headache diary application.

Headache days of at least moderate severity will be derived from the e-diary data as described in Section 6.1.1. The 12-week period is the period from administration of the first dose of IMP to the EODBT as defined in Section 4.4. The monthly average number of headache days of at least moderate severity will be calculated using formula A. Missing data handling method is provided in Section 6.1.4.

### 6.2.2. Primary Efficacy Analysis

The hypothesis testing for the primary analysis is:

$$H_o : \delta_1 = \delta_2 \quad \text{vs} \quad H_a : \delta_1 \neq \delta_2$$

where  $\delta_1$  and  $\delta_2$  are the estimates of mean change from baseline in the monthly average number of headache days of at least moderate severity for the fremanezumab treatment group and the placebo group, respectively.

The primary endpoint will be analyzed using an ANCOVA method. The model will include treatment as fixed effect and the baseline monthly average number of headache days of at least moderate severity and the posttraumatic headache onset (<12 months and  $\geq$ 12 months) as covariates. The least square (LS) mean and SE for each treatment group, LS means and corresponding 95% confidence intervals for the treatment differences (fremanezumab - placebo), and associated p-values will be presented.

The analysis will be performed on the FAS and PP analysis sets.

#### Example SAS code for ANCOVA

```
PROC MIXED DATA=<name>;
  CLASS TRTP ONSET;
  MODEL CHG= BASE ONSET TRTP /S;
  LSMEANS TRTP /DIFF=CONTROL ("Placebo") CL ALPHA=0.05;
  ODS OUTPUT LSMEANS= <name> DIFFS= <name> ;
RUN;
```

Where TRTP denotes the planned treatment group; CHG denotes the change from baseline in the monthly average number of headache days of at least moderate severity; BASE denotes the baseline monthly average number of headache days of at least moderate severity; ONSET denotes the posttraumatic headache onset (<12 months and  $\geq$ 12 months). In bold are the SAS key words.

### 6.2.3. Sensitivity Analysis for the Primary Efficacy Endpoint

A sensitivity analysis will be conducted to explore the impact of missing data in the primary efficacy analysis.

MMRM analysis will be utilized to estimate the mean change from baseline (baseline period) in the monthly average number of headache days of at least moderate severity during the 12-week period after the first dose of IMP.

Postbaseline data will include data from 3 monthly analysis windows (Month 1, Month 2, and Month 3) derived using the algorithm described in Section 6.1.3.

The MMRM will include the posttraumatic headache onset (<12 months and  $\geq$ 12 months), treatment, month (3 levels), and month-by-treatment interaction as fixed effects and baseline monthly average number of headache days of at least moderate severity as a covariate. The unstructured covariance structure (UN) will be used to model intra-subject correlation. LS mean and SE for each treatment group, LS means and corresponding 95% confidence intervals for the treatment differences (fremanezumab - placebo), and the associated p-values from the overall results for treatment comparisons on the average of months 1 to 3 will be presented to support the primary analysis. Notes: if UN dose not converge, the hierarchy uses the first-order autoregressive structure [AR-(1)] and the compound-symmetry structure (CS).

Example SAS codes for MMRM analysis:

```
PROC MIXED DATA=<name> METHOD=REML;
  CLASS USUBJID TRTP ONSET AVISIT;
  MODEL CHG=BASE ONSET TRTP AVISIT TRTP*AVISIT/S;
  REPEATED AVISIT/ SUB=USUBJID TYPE=UN;
  LSMEANS TRTP TRTP*AVISIT/ DIFF CL ALPHA=0.05;
  ODS OUTPUT LSMEANS= <name> DIFFS= <name> ;
RUN;
```

Where TRTP denotes the planned treatment group; ONSET denotes the posttraumatic headache onset (<12 months and  $\geq$ 12 months); AVISIT denotes the analysis window; BASE denotes the baseline monthly average number of headache days of at least moderate severity; CHG denotes the change from baseline.

The analysis will be performed on the FAS.

### 6.3. Secondary Efficacy Endpoints and Analyses

The key secondary efficacy endpoints are listed in Section 1.2. Analyses will be based on the FAS and PP analysis sets.

#### 6.3.1. Proportion of Patients Reaching at Least 50% Reduction From Baseline in the Monthly Average Number of Headache Days of at Least Moderate Severity During 12-Week Period of Treatment with the IMP

This secondary efficacy endpoint will be analyzed using Cochran-Mantel-Haenszel (CMH) test stratified by the posttraumatic headache onset (<12 months and  $\geq$ 12 months). Descriptive statistics (count and percent) and p-value for Row Mean Scores difference will be presented.

The 12-week period is the period from the first dose of the IMP to the EODBT as defined in Section 4.4. Headache during the 12-week period will be derived from the e-diary data as described in Section 6.1.1. The monthly average number of headache days of at least moderate severity will be calculated using formula A. Missing data handling methods are provided in Section 6.1.4 .

The proportion of reduction for a patient will be calculated using formula B. Responders will be those with  $\geq$ 50% reduction.

Example SAS code for CMH:

```
PROC FREQ DATA=<name>;  
    TABLES ONSET*TRTP*AVALC / CMH;  
    OUTPUT OUT=<name> CMH;  
RUN;
```

Where TRTP denotes the planned treatment group; ONSET denotes posttraumatic headache onset (<12 months and  $\geq$ 12 months); and AVALC denotes the responses with yes for responders (with  $\geq$ 50% reduction) and no for non-responders (with <50% reduction).

#### 6.3.2. Proportion of Patients Reaching at Least 50% Reduction From Baseline in the Monthly Average Number of Headache Days of at Least Moderate Severity During First 4-Week, 5- to 8-Week, and 9- to 12-Week Periods of Treatment with the IMP

The following endpoints will be analyzed using CMH test in a manner analogous to the analysis described in Section 6.3.1, respectively.

- proportion of patients reaching at least 50% reduction from baseline (baseline period) in the monthly average number of headache days of at least moderate severity during the first 4-week period after the first dose of the IMP
- proportion of patients reaching at least 50% reduction from baseline (baseline period) in the monthly average number of headache days of at least moderate severity during the 5- to 8-week period after the first dose of the IMP

- proportion of patients reaching at least 50% reduction from baseline (baseline period) in the monthly average number of headache days of at least moderate severity during the 9- to 12-week period after the first dose of the IMP

Postbaseline data will include data from 3 monthly analysis windows (Month 1/1- to 4-Week, Month 2/5- to 8-week, and Month 3/9- to 12 week) derived using the algorithm described in Section 6.1.3. Data in each analysis window will be prorated to 28 days using formula A. Headache of at least moderate severity within each analysis window will be derived from the e-diary data as described in Section 6.1.1. The proportion of reduction for a patient will be calculated using formula B for each analysis window. Responders will be those with  $\geq 50\%$  reduction.

### **6.3.3. Mean Change from Baseline in the Number of Headache Days of at Least Moderate Severity During the First 4-Week, 5- to 8-Week, and 9- to 12-Week Periods after the First Dose of the IMP**

The following endpoints will be analyzed using MMRM method in a manner analogous to the analysis described in Section 6.2.3.

- mean change from baseline (baseline period) in the number of headache days of at least moderate severity during the first 4-week period after the first dose of the IMP
- mean change from baseline (baseline period) in the number of headache days of at least moderate severity during the 5- to 8-week period after the first dose of the IMP
- mean change from baseline (baseline period) in the number of headache days of at least moderate severity during the 9- to 12-week period after the first dose of the IMP

Postbaseline data will include data from 3 monthly analysis windows (Month 1/1- to 4-Week, Month 2/5- to 8-week, and Month 3/9- to 12 week) derived using the algorithm described in Section 6.1.3. Data in each analysis window will be prorated to 28 days using formula A. Headache of at least moderate severity within each analysis window will be derived from the e-diary data as described in Section 6.1.1.

Results for each endpoint will be separated from PROC MIXED outputs. The results from the last analysis window will be presented.

### **6.3.4. Mean Change From Baseline in Disability Score, as Measured by the 6-Item Headache Impact Test (HIT-6) at Week 12 After the First Dose of the IMP**

The HIT-6 (Appendix B) is a tool used to measure the impact headaches have on a patient's normal daily life and ability to function. The HIT-6 consists of 6 items, including pain, social functioning, role functioning, vitality, cognitive functioning, and psychological distress. Each item is answered on a 5-point Likert scale (6 = never, 8 = rarely, 10 = sometimes, 11 = very often, or 13 = always), which are summed to produce a total score that ranges from 36 to 78, with larger scores reflecting greater impact of headache on the daily life of the patient.

During the double-blind treatment period patients will complete the HIT-6 questionnaire at visit 2 and visit 5/week 12 before the administration of the IMP or at ET visit.

The HIT-6 total score mean change from baseline at visit 5/week 12 will be analyzed using an ANCOVA method in a manner analogous to the analysis described in Section 6.2.2.

Categorical and numerical responses for each of 6-item questions will be summarized using descriptive statistics by visit.

**6.3.5. Mean Change From Baseline in the Assessment of Patient Satisfaction, as Measured by the Patient Global Impression of Change Scale, at 4, 8, and 12 Weeks after the First Dose of the IMP**

The PGIC is a validated generic tool for the assessment of overall change in the severity of illness following treatment.

During the double-blind treatment period patients will complete the HIT-6 questionnaire at visit 2 and visit 5/week 12 before the administration of the IMP or at ET visit.

During the double-blind treatment period, at visit 2/week 0, visit 3/week 4, visit 4/week 8, visit 5/week 12 before the administration of the IMP or at ET visit, patients will rate how they feel compared with how they felt before receiving IMP using the following 7-point scale:

- 1=No change (or condition has got worse)
- 2=Almost the same, hardly any change at all
- 3=A little better, but no noticeable change
- 4=Somewhat better, but the change has not made any real difference
- 5=Moderately better, and a slight but noticeable change
- 6=Better, and a definite improvement that has made a real and worthwhile difference
- 7=A great deal better, and a considerable improvement that has made all the Difference

For analysis purposes, a dichotomous scale of ‘Yes’ or ‘No’ will be derived. A favorable change is score of 5-7, which means there is significant improvement (Yes) with the treatment. If the response is 1-4, it is considered no significant improvement (No).

The percentage of patients’ dichotomous scale of ‘Yes’ or ‘No’ of PGIC assessments at baseline (week 0/visit 2), weeks 4, 8, and 12 (visits 3 to 5) will be analyzed using a CMH method in a manner analogous to the first secondary endpoint described in Section 6.3.1. Missing data will not be imputed.

Raw data for these visits will be summarized using descriptive statistics. Missing category will be presented if applicable.

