#### 9.5.5.3. Secondary Efficacy Analysis

The continuous secondary efficacy endpoints will be analyzed using an ANOVA method or a mixed-model for repeated measures. For the proportion of responders defined as 50% or more reduction from baseline in the monthly average headache days, the Cochran-Mantel-Haenszel test will be used stratified by PTH onset (<12 months and ≥12 months). For the key secondary endpoints, a 95% confidence interval will be constructed to compare the treatment effect between the fremanezumab group and the placebo group, and the p-value will be presented.

Testing of statistical significance at a 2-sided alpha of 0.05 will be performed for the primary endpoint. If the primary endpoint meets statistical significance, then each of the key secondary endpoints will be tested for significance in a pre-specified order at a 2-sided alpha of 0.05. If and when any p>0.05, no further comparisons will be interpreted inferentially. Details will be presented in the statistical analysis plan.

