### 1.2. Secondary Efficacy Endpoints

The secondary efficacy endpoints are:

- proportion of patients reaching at least 50% reduction from baseline (*baseline* period) in the monthly average number of headache days of at least moderate severity during the *12-week* period of treatment with the IMP
- proportion of patients reaching at least 50% reduction from baseline (baseline period) in the monthly average number of headache days of at least moderate severity during the first 4-week period after the first dose of the IMP
- proportion of patients reaching at least 50% reduction from baseline (baseline period) in the monthly average number of headache days of at least moderate severity during the 5- to 8-week period after the first dose of the IMP
- proportion of patients reaching at least 50% reduction from baseline (baseline period) in the monthly average number of headache days of at least moderate severity during the 9- to 12-week period after the first dose of the IMP
- mean change from baseline (*baseline* period) in the number of headache days of at least moderate severity during the first 4-week period after the first dose of the IMP
- mean change from baseline (*baseline* period) in the number of headache days of at least moderate severity during the 5- to 8-week period after the first dose of the IMP
- mean change from baseline (*baseline* period) in the number of headache days of at least moderate severity during the 9- to *12-week* period after the first dose of the IMP
- mean change from baseline (visit 2) in disability score, as measured by the 6-item Headache Impact Test (HIT-6) at week 12 after the first dose of the IMP
- mean change from baseline (visit 2) in the assessment of patient satisfaction, as measured by the Patient Global Impression of Change scale, at 4, 8, and 12 weeks after the first dose of the IMP

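### SAP 6.3.5 tests the 7-point PGIC only as 5-7 versus 1-4; a full-scale stratified test would fit the named endpoint better and, under a common shift of about 0.35-0.6 SD, have roughly 8-19 points more power per visit

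*SAP*

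**What the plan says.** For three post-dose time points (weeks 4, 8 and 12), SAP Section 1.2 lists this secondary efficacy endpoint: "mean change from baseline (visit 2) in the assessment of patient satisfaction, as measured by the Patient Global Impression of Change scale". Protocol Sections 2.1 and 9.5.2 name it in the same way.

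SAP Section 6.3.5 gives the seven response levels and then derives a Yes/No variable. Scores of 5 to 7 are Yes: "A favorable change is score of 5-7, which means there is significant improvement (Yes) with the treatment". Scores of 1 to 4 are No. The Yes/No percentages "will be analyzed using a CMH method in a manner analogous to the first secondary endpoint described in Section 6.3.1". That section specifies a Cochran-Mantel-Haenszel (CMH) test "stratified by the posttraumatic headache onset" (under 12 months versus 12 months or more), and the "p-value for Row Mean Scores difference will be presented". The ungrouped PGIC scores are summarized descriptively, and missing values are not imputed.

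For secondary endpoints in general, Protocol Section 9.5.5.3 says: "The continuous secondary efficacy endpoints will be analyzed using an ANOVA method or a mixed-model for repeated measures". It then names the CMH test for the 50% headache-day responders. It does not mention a PGIC split. SAP Section 17 lists no changes from the protocol's analyses.

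**The concern.** The endpoint is worded as a mean on an ordered scale, but the only inferential analysis compares two percentages. A move from 1 to 4, or from 5 to 7, adds nothing to the test. The row-mean-scores statistic that SAP 6.3.1 already asks for accepts ordered scores with more than two levels, so the cut is not needed to run the stratified test. The SAP gives no reason for the cut beyond calling 5-7 a favorable change.

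What is at stake is supportive patient-reported evidence in a proof-of-concept trial that stopped recruiting at 87 of 172 planned patients (Protocol Section 3.2). If the treatment shifts patients along the whole scale, the split makes that harder to see at each visit, and it saves no data. The point concerns the analysis scale at the post-dose visits. It does not depend on how the visit 2 score is used.

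**Working it through.** **The plan's own figure.** The documents give power only for the primary endpoint (sample-size wording in the Amendment 02 table, Protocol Section 16.1): difference 2.0 days, SD 4.4, two-sided alpha 0.05, 80% power, 77 evaluable per arm.
- Normal approximation: n = 2(1.960 + 0.842)² × (4.4/2.0)² = 76 per arm. The noncentral t gives 77, with power 0.800.
- With 10% dropout: 77/0.9 = 85.6, so 86 per arm and 172 in total. The figure reproduces.

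**Inputs for PGIC.** From the documents: 87 patients at 1:1 (43 and 44), or about 39 per arm after 10% dropout (43 × 0.9 = 38.7); two onset strata; alpha 0.05. Assumed, because the documents are silent: five placebo distributions with 18% to 60% scoring 5-7, stratum splits from 20:80 to 50:50, and the size and shape of the effect. The primary endpoint's standardized effect, 2.0/4.4 = 0.455 SD, is borrowed as one value of a latent normal shift. It is not a PGIC estimate.

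**One case by hand.** Take a placebo distribution uniform over 1-7, a shift of d = 0.4545 and n = 43 per arm, ignoring strata.
- *Split.* p0 = 3/7 = 0.429. The threshold is Φ⁻¹(4/7) = 0.180, so p1 = 1 − Φ(0.180 − 0.4545) = 0.608, and p̄ = 0.518. Power = Φ{[(p1 − p0)√n − 1.96√(2p̄(1 − p̄))] / √(p0(1 − p0) + p1(1 − p1))} = Φ{(1.178 − 1.385)/0.695} = 0.38.
- *Full scale.* Means 4.000 and 4.853, SDs 2.000 and 1.908, pooled SD 1.955. Power = Φ{(0.853/1.955)√(43/2) − 1.96} = Φ(0.063) = 0.525.
- The loss is about 14 points.

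**Simulation of the stratified CMH tests** (20,000 trials per case, common latent shift, ranges over the assumed placebo distributions):

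| Shift (SD) | Full scale, 43/arm | Split, 43/arm | Loss, 43/arm | Loss, 39/arm |
|---|---|---|---|---|
| 0.2 | 13-15% | 10-12% | 2-4 | 2-4 |
| 0.3 | 24-27% | 17-19% | 6-8 | 4-8 |
| 0.35 | 32-34% | 21-24% | 9-11 | 7-10 |
| 0.455 | 49-52% | 33-37% | 13-16 | 10-15 |
| 0.6 | 73-75% | 54-58% | 17-19 | 14-19 |

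A separate run at 43 versus 44 gives losses of 8-12, 11-16 and 15-20 points at 0.35, 0.455 and 0.6. The ends move by a point or so with the stratum counts and placebo distributions. Proportional-odds shifts (log odds ratio 0.8 to 1.1) lose 12-19 points. Type I error is about 5% for both tests.

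**Changing the shape of the effect.**
- If 30% of non-responders are moved into 5-7, the split wins by about 4-9 points across the five placebo distributions. For example, with 18% Yes on placebo, 0.18 + 0.3 × 0.82 = 43% Yes on drug, and power is 72% for the split against 63% for the full scale. Variants of this pattern give the split an advantage of about 3-14 points.
- If the effect is concentrated exactly at the cut, power is 22-38% for the split against 7-10% for the full scale.
- If the benefit stays within scores 1-4, the split has only its 5% false-positive rate, while the full scale has 6-43%.

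**The case against.** The cut is not arbitrary. In SAP 6.3.5 every level from 1 to 4 is worded as no noticeable or no real difference, and 5 is the first level described as noticeable. This is a pre-specified, readable responder definition, and citing no guideline for it is not a defect. This stands, and it is a reason to keep the 5-7 proportion and its test in the report. It does not explain why the split should be the only test of an endpoint named as a mean change.

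A reader might infer that the split breaks the protocol because Section 9.5.5.3 sets CMH aside for headache-day responders. The text does not go that far. It names CMH for those responders without excluding it elsewhere. Protocol Section 9 leaves changes and details to the SAP, and the SAP introduction says the SAP prevails. The ANOVA/mixed-model sentence covers continuous endpoints, and a seven-level rating is arguably not one. What remains is a mismatch between the endpoint's name and its test.

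It can also be objected that pairing a modified-ridit p-value with a mean difference would report an estimate of something other than what was tested, and that a mean assumes equal spacing on a scale whose lowest level merges no change with worsening. Both are fair. The first is met by matching the estimate to the scores. The second is a limitation to state if table scores are used.

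**Conclusion.** The concern holds as a conditional loss of efficiency and a poor fit to the named endpoint. With about 43 patients per arm and a common latent shift of about 0.35-0.6 SD, testing only 5-7 versus 1-4 costs roughly 8-19 points of power at each visit (13-16 points at the borrowed 0.455 SD). The placebo distributions, the shift and its common form are assumptions.

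Two stronger readings are tempting. The first is that the split costs this much power whatever the drug does. The documents contain no PGIC distribution, effect size or power, the loss is only 2-4 points at 0.2 SD, and the sign reverses if the effect consists of moving non-responders into 5-7. The second is that a controlled claim is at risk, because SAP 6.3 calls the Section 1.2 endpoints key secondary. The fixed sequence in SAP Section 7 stops at HIT-6, so the PGIC p-values are nominal and the family-wise error rate is unaffected. The change is worth making because it is cheap and information is scarce; the trial's main conclusion does not depend on it.

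**What to change.** In SAP 6.3.5, make the main PGIC test at weeks 4, 8 and 12 the onset-stratified CMH row-mean-scores test on the full 1-7 score, using the same observed cases. Fix in advance one of two matched pairs:
- default table scores (`TABLES ONSET*TRTP*PGIC / CMH`) with the stratified mean difference and 95% CI, which stays closest to the endpoint's wording; or
- modified ridits (`SCORES=MODRIDIT`, the van Elteren test) with the win probability and 95% CI.

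Keep the proportion scoring 5-7, with its CMH result, as a supportive responder summary, and label all PGIC p-values as nominal. SAP 2.5.2 has the SAP finalized before the double-blind database lock, so the choice belongs before that point.

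The cost is one SAP paragraph and one SAS statement. No new data are needed and the fixed sequence is untouched. The downside is one extra nominal result per visit and a main quantity that is slightly less simple to state than a percentage.

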A sample size of 154 patients (77 evaluable patients per treatment group) willwas calculated to provide 80% power to detect a treatment difference of 2.0 days in the monthly average (assuming a common SD of 4.4 days) at a 2-sided alpha level of 0.05. Assuming a 10% discontinuation rate, 172 patients (86 patients per treatment group) willwere planned to be randomized in the study.  Study recruitment was discontinued at 87 patients due to challenges to enrollment and not for any safety concerns.	A sample size of 154 patients (77 evaluable patients per treatment group) was calculated to provide 80% power to detect a treatment difference of 2.0 days in the monthly average (assuming a common SD of 4.4 days) at a 2-sided alpha level of 0.05. Assuming a 10% discontinuation rate, 172 patients (86 patients per treatment group) were planned to be randomized in the study.  Study recruitment was discontinued at 87 patients due to challenges to enrollment and not for any safety concerns.	Clarification to the sample size as study enrollment was discontinued due to challenges to recruitment prior to reaching the target sample size.
Section 9.2.4 Per-Protocol Analysis Set		I
The per-protocol (PP) analysis set is a subset of the ITT analysis set including only patients without any major protocol deviations or unexpected drug concentration findings. Major protocol deviations will be determined before unblinding and database lock.	The per-protocol (PP) analysis set is a subset of the ITT analysis set including only patients without any major protocol deviations. Major protocol deviations will be determined before unblinding and database lock.	The definition of the per-protocol analysis set was modified as this is a subset of patients who completed the study as intended, only with a lack of major protocol deviations.
In the PP analysis set, treatment will be assigned based on the treatment patients actually received, regardless of the treatment to which they were randomized.		

Original text with changes shown	New wording	Reason/Justification for change

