## 1.6. Estimand for Primary Efficacy Endpoint

The primary estimand for this study is defined by the following 4 components:

1. **Target population:** male and female patients aged 18 to 70 years, inclusive, with a history of PTH (as defined by International Classification of Headache Disorders 3rd revision [ICHD-3] (beta version) criteria).
2. **Outcome measure:** mean change from baseline (baseline period) in the monthly average number of headache days of at least moderate severity during the 12 week period after the first dose of the IMP.
3. **Analysis set and handling of intercurrent events:** The full analysis set (FAS) will be used for efficacy analyses. FAS is a subset of the ITT analysis set including only patients who received at least 1 dose of IMP and had at least 1 post-baseline efficacy assessment on the primary endpoint. In the FAS, treatment will be assigned based on the treatment to which patients were randomized, regardless of which treatment they actually received.

For patients randomized to active treatment who did not complete the double-blind treatment period due to lack of efficacy, death, or adverse event, the average number of headache days in the remainder of the analysis window will be imputed as the mean monthly average of headache days in the same analysis window for patients assigned to placebo.

All other missing data for patients in either treatment group will be handled as follows:

- For patients who have  $\geq 10$  days of e-diary data in an analysis window, the monthly average number of headache days will be calculated based on data available in that analysis window and prorated to 28 days
- For patients who have  $< 10$  days of e-diary data in an analysis window, the monthly average number of headache days will be imputed using the mean monthly average of

headache days in the same analysis window for patients assigned to the same treatment group and having  $\geq 10$  days of e-diary data.

More details are provided in Section [6.1.4](#).

4. **Measure of treatment effect:** analysis of covariance model including treatment as fixed effect and the baseline number of headache days of at least moderate severity and the posttraumatic headache onset ( $< 12$  months and  $\geq 12$  months) as covariates.

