**Table 1: Study Visits**

Visit #	V1 (Screening)	Double-Blinded Treatment Period			Open-Label Period			
		V2 	V3	V4	V5 	V6	V7	V8
Day	-28 to-1	0±3	28±3	56±3	84±3	112±3	140±3	168±3
Week	-	0	4	8	12	16	20	24
	Visit 1	Visit 2 Dose 1	Visit 3/ Dose 2	Visit 4/ Dose 3	Visit 5/ Dose 4/ EODBT	Visit 6/ Dose 5	Visit 7/ Dose 6	Visit 8/ EOT/EOS/ET 

 Baseline/Randomization

 Visit 5 is the end of double-blind treatment period and the beginning of open-label period

 EOT=the end of treatment; EOS=end of study; ET=early termination

The end of double-blind treatment period (EODBT) is defined as Visit 5/Week 12 or early termination (ET) visit for patients did not complete double-blind treatment period and did not continue in open-label period.

‘Last Assessment’ may be derived for analysis purpose for safety data and is defined as the last observed postbaseline data during the double-blind treatment period for double-blind period or the last observed postbaseline data during the open-label treatment period for open-label period.

For patients who withdraw from the study early, their data at the early withdrawal visit will be excluded from the by-visit summaries but will be included in the ‘Last Assessment’ summaries.

Study days are numbered relative to the first day of the IMP administration. The start of treatment (day 1) is defined as the date on which a patient takes the first dose of the IMP, as recorded on the case report form (CRF). Days will be numbered relative to treatment start (ie, ..., -2, -1, 1, 2, ...; with day 1 being the day of the first IMP administration and day -1 being the day before the day of the first IMP administration).

For data from the e-diary, monthly analysis windows [Month 1 (weeks 1 to 4), Month 2 (weeks 5 to 8), and Month 3 (weeks 9 to 12)] will be derived for the purpose of efficacy endpoint analyses. Details are provided in Section 6.1.3.

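### PGIC is tested only on patients who have a score, so those who stop before week 4 or week 8 leave those comparisons; a small, cheaply removed dependence on retention

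*SAP*

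**What the plan says.** **PGIC (SAP 6.3.5).** The seven-point score is split in two. On the upper side, "A favorable change is score of 5-7, which means there is significant improvement (Yes) with the treatment"; a No is assigned to a response of 1 to 4. The percentages at baseline and at weeks 4, 8 and 12 "will be analyzed using a CMH method in a manner analogous to the first secondary endpoint described in Section 6.3.1", that is, stratified by headache onset. The section then states "Missing data will not be imputed". A missing category is mentioned only for the descriptive summary of the raw scores.

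**Early withdrawals (SAP 4.4).** For patients who leave early, "their data at the early withdrawal visit will be excluded from the by-visit summaries".

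**Week 12 (SAP 6.1).** A patient with no visit 5 assessment who does not enter the open-label period, but who has an end-of-study assessment, has that assessment used as week 12. Withdrawing patients are to have the visit 8 procedures at their last visit (SAP 2.1), and PGIC is among them (Protocol Table 1 and Appendix H).

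**Headache-day responders (SAP 6.3.1, 6.3.2 and 6.1.4).** Section 6.3.1 says "Missing data handling methods are provided in Section 6.1.4", and 6.3.2 follows 6.3.1. A note in 6.1.4 extends its imputation to every efficacy endpoint based on the number of headache days. PGIC is not one of these.

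**Testing order (SAP 7).** The sequence is the primary endpoint, the 50% responder endpoint and HIT-6. PGIC is not in it.

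**The concern.** A missing score is neither Yes nor No, so it has no cell in the CMH table. SAP 6.1 names the full analysis set for efficacy, yet at weeks 4 and 8 the PGIC test uses only the members of that set still being assessed. Retention is a post-randomisation outcome that treatment can affect. If one arm loses more patients because they were not helped or could not tolerate the injections, that arm's observed response rate rises relative to the other arm's.

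The three percentages also rest on different patient sets. Someone who stops at week 2 and attends a final visit is absent at weeks 4 and 8 and present at week 12.

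Nothing else in the SAP covers this gap. The missing-data sensitivity analysis in 6.2.3 is for the primary endpoint only, and repeating PGIC on the per-protocol set does not bring these patients back.

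**Working it through.** **1. Who is lost, and when.**

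| Patient stops | Week 4 | Week 8 | Week 12 |
|---|---|---|---|
| before visit 3 | lost | lost | kept if a final-visit score exists |
| between visits 3 and 4 | kept | lost | kept if a final-visit score exists |
| after visit 4 | kept | kept | kept if a final-visit score exists |

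**2. What the headache-day responder endpoints do instead.** SAP 6.1.4 has three rules. These examples use assumed values.
- Active-arm patients who "did not complete the double-blind treatment period due to lack of efficacy, death, or adverse event": observed headache days plus placebo-average days for the rest of the window. With 3 headache days in 14 diary days and a placebo mean of 12: 3 + 14 × 12/28 = 9. From a baseline of 16, the reduction is 7/16 = 44%, a non-responder.
- Others with at least 10 diary days: prorated. With 3 headache days in 14: 3/14 × 28 = 6. From 16, the reduction is 10/16 = 62.5%, a responder.
- Others with fewer than 10 diary days: own-arm mean. With an arm mean of 10 and a baseline of 22, the reduction is 12/22 = 55%, a responder.

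These patients stay in the denominator, but they are not all scored as failures. The contrast with PGIC is imputed against dropped.

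**3. Inputs from the plan.** The documents give no PGIC response rate and no dropout by arm. The only dropout figure is in Protocol 16.1, new wording of Section 9.1: "Assuming a 10% discontinuation rate, 172 patients (86 patients per treatment group) were planned to be randomized in the study". It reproduces: 77/0.90 = 85.6, so 86 per group and 172 in total. Recruitment stopped at 87 patients (Protocol 3.2), and 10% of 87 is about 9. Allocation is 1:1, so take 43 v 44.

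**4. Assumptions.** Total 12-week dropout is 14% active v 5% placebo: 0.14 × 43 + 0.05 × 44 = 8.2 patients, or 9.4% of 87. Dropout accrues evenly, so one third has occurred by week 4 and two thirds by week 8. Response among observed patients is p in both arms, and all dropouts are unimproved.

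The observed-case difference is then 0. The all-patient difference is p(1 − d1) − p(1 − d2) = −p(d1 − d2), where d1 and d2 are the dropout fractions at that visit. The standard error (SE) is √{p(1 − p)[1/(43(1 − d1)) + 1/(44(1 − d2))]}.

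| Visit | d1 v d2 | Shift at p = 45% | SE (points) | Shift/SE | Shift at p = 35% to 55% |
|---|---|---|---|---|---|
| Week 4 | 4.7% v 1.7% | 0.45 × 3.0 = 1.4 points | 10.8 | 0.12 | 1.1 to 1.7 |
| Week 8 | 9.3% v 3.3% | 0.45 × 6.0 = 2.7 points | 11.0 | 0.24 | 2.1 to 3.3 |
| Week 12, nobody attends a final visit | 14% v 5% | 0.45 × 9.0 = 4.0 points | 11.2 | 0.36 | 3.2 to 5.0 |

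A wider 16% v 4% split at p = 45% gives 0.45 × 4.0 = 1.8 points, 0.45 × 8.0 = 3.6 points and 0.45 × 12.0 = 5.4 points. Reversing the imbalance reverses the sign.

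**5. Equal dropout.** With d1 = d2 and equal response the difference is unbiased. If response differs, the observed-case difference is larger than the all-patient one: with 10% missing in each arm, 50% v 30% among observed patients is 20.0 points, against 0.9 × 20 = 18.0 points over all patients.

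**6. Nominal test.** With all-patient response of 40% in both arms and the 14/5 split, simulation of the observed-case test rejects at about 5.2% at week 4, just under 6% at week 8, and about 7% at week 12 if nobody attends a final visit.

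**The case against.** The strongest reply is that an observed-case analysis of a nominally tested patient-reported outcome, stated in advance, is a legitimate choice in a phase 2 proof-of-concept trial, and that little hangs on it. Much of this stands. Week 12 is largely protected by SAP 6.1, the shifts are a fraction of a standard error, and PGIC carries no controlled alpha. The rejection rates in step 6 arise because the observed response rates then truly differ (46.5% v 42.1% at full dropout), so they are not a fault in the test itself.

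The proposed rule is open to criticism too. It scores every stop as No, including stops unrelated to response, and it is not the SAP 6.1.4 method either.

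What remains is that the planned comparison at weeks 4 and 8 depends on retention, and that no supportive analysis shows how much.

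Three stronger readings are tempting but unsupported:
- A reader might infer that the SAP's other responder endpoints count dropouts as non-responders. Step 2 shows that they do not.
- A reader might infer that early stoppers vanish from PGIC altogether. SAP 6.1 returns those with a final-visit score at week 12.
- A reader might apply the whole 12-week dropout to every visit and conclude that the bias is 4 to 5 points throughout. Patients who stop later still have scores at weeks 4 and 8.

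**Conclusion.** The point holds in limited form. As written, SAP 6.3.5 makes the week 4 and week 8 PGIC comparisons conditional on still being in the study, and the week 12 comparison conditional on having a visit 5 or final-visit score. The comparison can be biased if early stopping differs by arm.

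On the 14% v 5% split, even accrual, 45% response and unimproved dropouts, the bias is about 1.4 points at week 4 and 2.7 at week 8. About 4 points is the upper bound at week 12 under those assumptions. Only the 10% overall dropout, the 87 patients and the 1:1 ratio come from the documents.

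The primary conclusion and the error control of SAP 7 are untouched, because PGIC is outside the sequence. This is a worthwhile, inexpensive improvement to a nominal secondary analysis.

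**What to change.** In SAP 6.3.5, replace the no-imputation sentence with wording to this effect: all full-analysis-set patients are included at weeks 4, 8 and 12; a patient with no PGIC score at a visit because double-blind treatment was stopped counts as No at that visit, and at week 12 this applies only when no end-of-study assessment is available under SAP 6.1. Keep the observed-case CMH test as a supportive analysis, and report the denominator by arm at each visit.

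The cost is a short change to one section and one extra table, to be settled before the double-blind database lock so that the rule cannot look data-driven. The downside is slightly lower reported response rates and a No for some patients who stopped for unrelated reasons. The observed-case table lets readers judge how much that matters.
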